5.3 Explanatory Variables and Additional Analyses

These include demographic and clinical variables (such as age, gender, history of prior exposure, age at first exposure, duration of opioid therapy, use of concomitant medications, etc.) in order to identify possible risk factors for development of opioid tolerance during PICU therapy, and to generate hypotheses for future studies. In addition, since some opioid drugs are highly lipophilic (e.g. fentanyl) and others are not (e.g. morphine), we will calculate BMI and ideal body weight to evaluate the impact of increasing obesity on opioid tolerance.

In exploratory analyses, we will also assess rates of the primary and secondary endpoints according to other explanatory study variables. Factors examined in these analyses will include age, gender, history of prior exposure, age at first exposure, duration of opioid therapy, use of concomitant medications, and BMI. For continuous factors, categories will be defined using clinically appropriate cut-points, or quartiles of the observed data when such cut-points do not exist or are equivocal. Chi-squared tests or exact analogues will be used to compare proportions achieving the endpoint between subgroups. Logistic regression models will be used to assess factors that are independently predictive of tolerance, starting with candidate factors showing at least a weak statistical trend toward unadjusted association with the endpoint.

This study will be collecting information on other outcomes, for example, clinical status at PICU discharge and other clinical variables. The general strategy for analyses of other outcomes collected in this study will follow that specified for the primary and secondary study endpoints. Other binary or categorical outcomes such as PICU and hospital survival will be compared using chi-square tests or exact analogues. For other continuous outcome variables, summary statistics and box-plots will be used to investigate their distributions. Where indicated in order to ensure satisfaction of assumptions, we will either use transformations or non-parametric statistics.

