Univariate and multivariable regression analyses as described above (logistic for binary outcome, and linear regression for continuous outcomes appropriately transformed when necessary) will be used to assess the effects of covariates such as age, gender, and race. Tolerance-related parameters, such as time to doubling of the opioid dose, may be used as predictors in selected analyses. For outcomes recorded as integral days, such as time in PICU, we will also examine Poisson regression analyses using the SAS GENMOD procedure.

Exploratory repeated measures analyses will make use of the daily data elements collected in this study to assess patterns of opioid dosing across time, and examine factors associated with differences in such patterns. The general linear mixed model will be used for these analyses, to control for within-subject correlation of observations across time, and to appropriately model trajectories. Polynomial or spline models may be used as appropriate in these exploratory analyses to allow maximum flexibility in modeling observed patterns of dosing or response across time.

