5.4 Sample Size Estimates and Effect on Analysis

A conservative estimate of 450 subjects would be expected to yield a 95% confidence interval for proportion of opioid tolerance with precision ranging from 4-5%. We would expect 80% power to detect absolute differences in outcome rates of 14% or higher in exploratory comparisons between two subgroups of about equal size. In terms of ability to fit multivariable models, assuming an outcome rate of at least 25%, we would be able to fit models with up to 10 variables or factor levels, using the common "ballpark rule" of at least 10 events per factor in a logistic regression model. These analyses will refine the design of a randomized controlled trial and provide incidence estimates that are fairly accurate, in order to assist with the sample size calculations for a proposed intervention trial. In addition, clinical factors identified by the proposed multivariable analyses that are independently predictive of the primary outcome (or secondary outcomes) can be used for stratified enrollment in future clinical trials.

6 Accrual Projections and Duration of Study

At the CPCCRN centers from 2004-2006, there were 6,838 mechanically ventilated pediatric patients who did not require ECMO in the PICU. We propose enrollment of 450 subjects, a sample size that will permit estimation of the incidence of opioid tolerance with a precision of 4 to 5%. This sample will provide 80% power to detect outcome differences of 14% or higher in exploratory comparisons between subgroups of approximately equal size. The accrual period is anticipated to be up to 12 months.

7 Site Monitoring

Site monitors may visit each site at initiation, at a frequency to be determined by the DCC and National Institute for Child Health and Human Development (NICHD). The purposes of these visits are to help assure regulatory compliance at all sites, to improve the quality of data collection and management at each site, and to provide education to site coordinators and investigators (if needed). The site monitors may be hired by the DCC via a subcontract, and monitoring reports will be sent to the DCC.

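### Poisson regression is named for whole-day outcomes with no provision for over-dispersion, so standard errors in this supplementary analysis may be too small (minor)

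*Protocol*

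**What the plan says.** Section 5.3 covers explanatory variables and additional analyses. Its general route for regression is logistic models for binary outcomes and "linear regression for continuous outcomes appropriately transformed when necessary". For outcomes counted in whole days, with time in PICU as the example, it then adds: "we will also examine Poisson regression analyses using the SAS GENMOD procedure". The covariates named just before that sentence are examples only: the regressions "will be used to assess the effects of covariates such as age, gender, and race".

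The same section has a general safeguard for other continuous outcomes: "Where indicated in order to ensure satisfaction of assumptions, we will either use transformations or non-parametric statistics". Section 5.2 makes linear regression of the secondary outcomes conditional on a satisfactory fit. Neither section mentions over-dispersion, a scale parameter, robust standard errors or negative binomial regression. Nor does either say that the Poisson dispersion will be held at 1.

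Time in PICU is neither the primary endpoint (Section 3.3) nor one of the three secondary endpoints (Section 3.4). One purpose of the explanatory analyses is "to generate hypotheses for future studies".

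**The concern.** Length of stay is not a count of independent events at a common rate. The eligible children range from 37 weeks post-conceptional age to under 18 years (Section 3.6.1). The diagnostic list runs from asthma to sepsis, trauma and transplant, with and without surgery (Section 4.2). Differences in expected stay that the covariates do not explain push the variance of a day count above its mean. A Poisson model with its standard errors left as they come would then report intervals that are too narrow and p-values that are too small.

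The safeguards elsewhere do not reach this model. Transforming the outcome or using a rank test replaces the Poisson model; it does not correct a Poisson standard error. Being exploratory excuses a lack of multiplicity control, but it does not make a wrong standard error right. At stake is the credibility of any factor reported as associated with days in PICU from this model.

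**Working it through.** **Plan's own figure.** There is none to reproduce. The protocol gives no mean, SD, dispersion or number of tests for the Poisson analysis.

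**Inputs from the protocol.** N = 450 (Section 5.4). Daily collection stops at Study Day 14 at the latest (Section 4.3), and exit day is recorded as 1 to 14 (Section 4.4).

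**Assumed.** The variance-to-mean ratio, written φ, and two equal groups of 225.

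**Step 1: formula.** The unscaled Poisson standard error is the true one divided by √φ. The actual two-sided error of a nominal 5% test is therefore 2 × (1 − Φ(1.96/√φ)).

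| Assumed φ | Poisson SE as share of true SE | 1.96/√φ | Actual type I error |
|---|---|---|---|
| 1 | 1.00 | 1.96 | 5% |
| 1.5 | 0.82 | 1.60 | 11% |
| 2 | 0.71 | 1.39 | 17% |
| 3 | 0.58 | 1.13 | 26% |

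**Step 2: simulation.** Log-normal stays were rounded up to whole days, with 225 per group, no true difference and 3,000 runs per scenario. Each scenario was run with stay capped at 14 days and again uncapped.

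| Median (days), log-SD | φ capped | Unscaled Poisson, capped | φ uncapped | Unscaled Poisson, uncapped |
|---|---|---|---|---|
| 5, 0.6 | 1.65 | 12.5% | 2.41 | 19.2% |
| 7, 0.6 | 1.60 | 12.2% | 3.43 | 28.9% |
| 7, 0.8 | 2.09 | 18.4% | 8.15 | 48.8% |
| 7, 1.0 | 2.47 | 20.7% | 18.96 | 65.3% |

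The formula agrees with the simulation. For example, φ = 2.09 gives 1.96/1.446 = 1.356 and an error of 17.5%, against 18.4% simulated.

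**Step 3: how large φ can be inside the window.** A variable bounded between 1 and 14 with mean m has variance at most (14 − m)(m − 1). At m = 8 this is 6 × 7 = 42, so φ ≤ 42/8 = 5.25. Over all means, φ ≤ 15 − m − 14/m. This is largest at m = √14 ≈ 3.74, where it is 15 − 2√14 ≈ 7.5. These limits are reached only if every child has exactly 1 or exactly 14 days, so realistic values lie well below them.

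**Step 4: effect of the remedy.** In the same eight scenarios, Pearson-scaled and robust standard errors gave a type I error of 4.5% to 5.6%. Linear regression on log days, which fits the protocol's own transformed-linear route, gave 4.5% to 5.3%.

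**The case against.** The strongest reply is that the sentence does not commit to an unscaled model. Poisson regression with a scaled or robust variance is still Poisson regression in the same procedure. The choice of option is a detail that a statistical analysis plan, not available here, may settle. This has weight, and it is why the point is not a claim that the analysis will go wrong. What remains is that the protocol names a model with a known weakness for this kind of outcome. It attaches a fit condition to the linear models for secondary outcomes but none to this one.

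The second reply is that this is an additional look beside transformed linear regression. That is correct, and it limits the severity.

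A reader might infer three stronger things that the documents do not support:

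- **Many factors will appear significant by chance.** With seven null factors, the expected number of false positives is 7 × 0.11 = 0.8 at φ = 1.5 and 7 × 0.17 = 1.2 at φ = 2. It nears 4 only at φ = 10, where the error is 54%. The seven come from the list for the primary and secondary endpoints ("Factors examined in these analyses will include age, gender, history of prior exposure, age at first exposure, duration of opioid therapy", plus concomitant medications and BMI). Beside the Poisson sentence only age, gender and race are named.
- **About half of all null tests will reject.** That needs φ near 8, for example a mean of 8 days with an SD of 8. Step 3 rules this out for recorded study days, so it would require stay counted past day 14.
- **The design of future trials will be distorted.** Section 5.4 says that identified factors "can be used for stratified enrollment in future clinical trials", but it limits this to predictors of the primary or secondary outcomes. Time in PICU is neither. Duration of exposure is a secondary endpoint but is specified in hours, not whole days.

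**Conclusion.** The point holds as a minor one. Section 5.3 names Poisson regression for whole-day outcomes and makes no provision for variance above the mean. Under the assumed log-normal stays limited to 14 days (φ about 1.6 to 2.5), a nominal 5% test rejects about 12% to 21% of the time under the null. In the uncapped scenarios it rejects 19% to 65% of the time. Both ranges rest on assumed distributions and on the dispersion being left at 1, which the protocol neither states nor excludes. The primary result, the defined secondary endpoints and the logistic risk-factor model are not affected.

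**What to change.** In Section 5.3, change the model named for whole-day outcomes to: *Poisson regression with Pearson-scaled or robust variance (or negative binomial regression if over-dispersed) using the SAS GENMOD procedure*. Scaled or robust variance is the safer of these options, because days may be capped at 14 and a capped count need not follow a negative binomial form.

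The cost is one clause in the text and one model option in the same procedure, with no new data. The only downside is wider, correct intervals.

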5.4 Sample Size Estimates and Effect on Analysis

A conservative estimate of 450 subjects would be expected to yield a 95% confidence interval for proportion of opioid tolerance with precision ranging from 4-5%. We would expect 80% power to detect absolute differences in outcome rates of 14% or higher in exploratory comparisons between two subgroups of about equal size. In terms of ability to fit multivariable models, assuming an outcome rate of at least 25%, we would be able to fit models with up to 10 variables or factor levels, using the common "ballpark rule" of at least 10 events per factor in a logistic regression model. These analyses will refine the design of a randomized controlled trial and provide incidence estimates that are fairly accurate, in order to assist with the sample size calculations for a proposed intervention trial. In addition, clinical factors identified by the proposed multivariable analyses that are independently predictive of the primary outcome (or secondary outcomes) can be used for stratified enrollment in future clinical trials.

6 Accrual Projections and Duration of Study

At the CPCCRN centers from 2004-2006, there were 6,838 mechanically ventilated pediatric patients who did not require ECMO in the PICU. We propose enrollment of 450 subjects, a sample size that will permit estimation of the incidence of opioid tolerance with a precision of 4 to 5%. This sample will provide 80% power to detect outcome differences of 14% or higher in exploratory comparisons between subgroups of approximately equal size. The accrual period is anticipated to be up to 12 months.

7 Site Monitoring

Site monitors may visit each site at initiation, at a frequency to be determined by the DCC and National Institute for Child Health and Human Development (NICHD). The purposes of these visits are to help assure regulatory compliance at all sites, to improve the quality of data collection and management at each site, and to provide education to site coordinators and investigators (if needed). The site monitors may be hired by the DCC via a subcontract, and monitoring reports will be sent to the DCC.

During the site monitor visit, the monitor will inspect the Essential Documents Binder at each site. This binder contains IRB documents, investigator licenses, and other required materials. The contents of the EDB are a topic included in the training for each site. The monitor will examine the IRB documents, and will verify that the IRB approval is valid for the current version of the MOTIF study protocol. The monitor will also examine subject study files.

Source verification will be done on selected data elements, as 100% source verification is extremely expensive. The DCC will prepare lists of specific data elements to be verified. These lists will remain confidential to the DCC until completion of MOTIF to prevent the site from predicting the data elements that will be inspected by the monitor.

The monitor will also discuss the study protocol and workflow with staff at the clinical site, and will try to verify that the site is maintaining an appropriate level of expertise and education in its research staff. This is a constructive goal, because when site monitors identify areas of confusion at clinical sites, the DCC will prepare additional training materials to address these specific domains.

Finally, the monitor will verify that the study protocol is being followed, and will help assure regulatory compliance at each site.

8 Remote Monitoring

The site monitoring described in Section 7 is very expensive, and will be supplemented with remote monitoring by DCC study coordinators. The DCC will prospectively identify selected data elements for remote monitoring on a quarterly basis. The selected data elements will be different for each quarter, for each site. This prospective plan will not be shared with other MOTIF investigators until the project is completed, in order that the research coordinator will not know what data will be monitored. The study coordinators will print out the data elements from TrialDB, and will then send a request for the site to fax the source documents for those data elements to a secure fax server at the DCC. The source documents will be compared with the TrialDB data entry. Sites that have high accuracy will be monitored less frequently than sites with less ideal performance. Sites with very poor accuracy on remote monitoring may have double data entry instituted for all data entry until accuracy improves to a satisfactory level.

9 Data Security and Backup

The DCC has a dedicated, locked 720 ft² server room within its offices, and the building has 24 hour on-site security guards. The DCC has a state-ofthe-art computer infrastructure and coordinates its network infrastructure and security with the Health Sciences Campus (HSC) information systems at the University of Utah. This provides the DCC with effective firewall hardware, automatic network intrusion detection, and the expertise of dedicated security experts working at the University. Communication over public networks is encrypted with virtual point-to-point sessions using secure socket layer (SSL) or virtual private network (VPN) technologies, both of which provide at least 128 bit encryption.

Direct access to DCC machines is only available while physically located inside the DCC offices, or via a VPN client. All network traffic is monitored for intrusion attempts, security scans are regularly run against our servers, and our IT staff are notified of intrusion alerts. Security is maintained with Windows 2003 user/group domain-level security. Users are required to change their passwords every 90 days, and workstations time out after 10 minutes of inactivity. All files are protected at group and user levels; database security is handled in a similar manner with group level access to databases, tables, and views in Microsoft SQL Server.

DCC production servers running critical applications are clustered and configured for failover events. Servers are backed up through a dedicated backup server that connects across an internal Gigabyte network to a robotic tape drive. Incremental backups occur hourly Monday through Friday from 6am to 6pm. Incremental backups also are performed each night with full system backups occurring every Friday. Tapes are stored in a fireproof safe inside the server room, and full backups are taken off site on a weekly basis to a commercial storage facility.

All personnel at the DCC have signed confidentiality agreements concerning all data encountered in the DCC. All personnel involved with DCC data systems have received Human Subjects Protection and HIPAA education.

10 Health Insurance Portability and Accountability Act (HIPAA)

The DCC computer systems adhere to requirements of HIPAA. The DCC has offered a Business Associate Agreement (BAA) to all CPCCRN sites. The BAA is not required for the research itself, but rather, for the possession of identifiable patient information and subsequent recoding into a de-identified analytical database. This latter activity is carried out on behalf of the Covered Entity (each clinical site).

11 Human Subjects

Waiver of informed consent will be requested for this study because the scientific validity of the study, to determine the true incidence of opioid tolerance among patients admitted to the PICU requires 100% of eligible patients over the study interval. The study fulfills regulatory requirements for a waiver, because there are no changes in clinical practice, no therapeutic interventions, only minimal risk to the patient (loss of privacy), and obtaining informed consent would threaten the scientific validity of the study.

All sites will obtain IRB approval, and provide documentation of such approval to the DCC, before any subject is entered into the study. All records will be kept in a locked/password protected computer. Clinical information will not be released without the written permission of the patient, except as necessary for data quality monitoring by the CPCCRN DCC, the National Institute for Child Health and Human Development (NICHD), or other governmental regulatory bodies.

This is an observational study with no intervention; adverse events that are associated with critical illness and PICU hospitalization will not be recorded in this study.

12 Record Retention

For federally funded studies subject to the Common Rule, records relating to the research conducted shall be retained for at least 3 years after completion of the research. Completion of the research for this protocol should be anticipated to include completion of all publications relating to the research. All records shall be accessible for inspection and copying by authorized representatives of the regulatory authorities at reasonable times and in a reasonable manner [45 CFR §46.115(b)].

Bibliography

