4.2 Study Entry and Day One Data Elements

The following data elements will be obtained and recorded when a patient is enrolled into the study:

- 1. Study Code ID
- 2. Clinical Center ID
- 3. Date of Enrollment
- 4. Date and Time of Admission to PICU
- 5. Gender
- 6. Race
 - American Indian or Alaska Native A person having origins in any of the original peoples of North and South America, including Central America, and who maintains tribal affiliation or community attachment.
 - Asian A person having origins in any of the original peoples of the Far East, Southeast Asia, or the Indian subcontinent, including, for example, Cambodia, China, India, Japan, Korea, Malaysia, Pakistan, the Philippine Islands, Thailand, and Vietnam.
 - **Black or African American** A person having origins in any of the black racial groups of Africa.
 - Native Hawaiian or Other Pacific Islander A person having origins in any of the original peoples of Hawaii, Guam, Samoa, or other Pacific Islands.
 - White A person having origins in any of the original peoples of Europe, the Middle East, or North Africa.
 - Other (provide text) Should provide text description.

Stated as Unknown Explicitly stated as unknown.

- 7. Ethnicity
 - Hispanic or Latino
 - Not Hispanic or Latino
 - Stated as Unknown
- 8. Date of Birth
- 9. Height (cm)
- 10. Weight (kg)

- 11. Admission Pediatric Risk of Mortality III (PRISM III) Score (Based on first 12 hours of PICU admission)
- 12. History of previous PICU admission (Yes or No)?
- 13. History of NICU admission (Yes or No)? If yes, duration in days.
- 14. History of surgical operation in previous hospitalizations (Yes or No)?
- 15. Primary Diagnostic Category (Select One)
 - Asthma (reactive airway disease)
 - Cancer
 - Cardiac arrest w/in 24 hours (closed chest massage)
 - Chromosomal abnormality
 - Diabetes
 - Drug overdose (e.g. ingestion, toxicity)
 - Gastroesophageal reflux
 - Cardiovascular disease acquired
 - Cardiovascular disease congenital
 - HIV infection
 - Hypoxic-ischemic encephalopathy of recent onset (acute, not static)
 - Medical device malfunction
 - Meningitis
 - Pneumonia / bronchiolitis
 - Seizures (includes complications of seizure therapy)
 - Sepsis
 - Shock
 - Suicide attempt (includes intentional drug overdose)
 - Transplant
 - Trauma
 - Other Diagnosis
- 16. Secondary Diagnostic Category (Select One)
 - Asthma (reactive airway disease)

- \bullet Cancer
- Cardiac arrest w/in 24 hours (closed chest massage)

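### The tolerance model offered as a source of strata for future trials draws on total opioid duration and later drug use, which are unknown at enrolment, and adjusting for duration can hide usable entry factors

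*Protocol*

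**What the plan says.** Protocol section 5.3 lists the factors to be examined as age, gender, prior exposure, age at first exposure, and then "duration of opioid therapy, use of concomitant medications, and BMI". It continues: "Logistic regression models will be used to assess factors that are independently predictive of tolerance". Candidates enter after showing some sign of an unadjusted association with tolerance. The section does not separate variables fixed at entry from those that accrue afterwards, and it does not limit concomitant drugs to day one.

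Section 5.4 states the later use. Clinical factors from these models that independently predict the primary outcome, or a secondary one, "can be used for stratified enrollment in future clinical trials". It also sets the size of the model: "we would be able to fit models with up to 10 variables or factor levels".

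Three other places bear on the point:

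- Sections 3.4 and 5.2 make duration of exposure a secondary endpoint, counted up to study exit.
- Section 3.1 hypothesises that tolerance is concentrated in children with four or more days of infusion.
- Section 4.2 collects a set of entry variables, among them "Admission Pediatric Risk of Mortality III (PRISM III) Score", and also records sedatives and analgesics given on the first study day. Section 4.3 records drug use on each later day.

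**The concern.** A stratification factor must be known when the child is enrolled. Total time on opioids is known only when opioids stop or the child leaves the study, and drugs given on later days are likewise unknown at the start. Section 5.4 nevertheless takes its strata from a model that may contain both.

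The second difficulty is less visible. Duration plausibly lies between entry characteristics and tolerance: a child who is expected to need longer therapy has more days on which a doubling can occur. Once duration is in the model, the coefficient of an entry factor measures only what remains at a given duration. An entry factor that raises tolerance by prolonging therapy can then look unimportant, although it is the sort of factor a later trial could stratify on. At stake is how well the tolerance model serves the design use that section 5.4 gives it.

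**Working it through.** **1. The plan's own figure.** The inputs, all from section 5.4, are "A conservative estimate of 450 subjects", "assuming an outcome rate of at least 25" per cent, and "at least 10 events per factor in a logistic regression model". Events = 450 × 0.25 = 112.5. With 10 parameters, 112.5 / 10 = 11.25 events each, so the stated limit of 10 is reproduced. A model restricted to entry variables uses the same events and keeps the same limit.

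**2. Will duration enter the model?** It is a screened candidate, not a fixed term. But section 3.1 makes longer infusion the expected driver of tolerance, and more days on opioids give more days on which a doubling can be seen. It is therefore very likely to pass an unadjusted screen.

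**3. The mechanism by hand.** The effects here are assumed; they are not protocol figures. Let X be an entry factor present in half the children, D long duration and Y tolerance:

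- logit P(D) = −0.75 + 1.5X
- logit P(Y) = −2.0 + 1.5D, so X has no direct effect

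Then:

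- P(D) = 0.321 for X = 0 and 0.679 for X = 1.
- P(Y) = 0.119 without and 0.378 with long duration, a difference of 0.258.
- P(Y | X = 0) = 0.119 + 0.321 × 0.258 = 0.202.
- P(Y | X = 1) = 0.119 + 0.679 × 0.258 = 0.295.
- Overall rate = (0.202 + 0.295) / 2 ≈ 25%, the rate section 5.4 assumes.
- Odds ratio without duration = (0.295 / 0.705) / (0.202 / 0.798) ≈ 1.65.
- Odds ratio at fixed duration = 1.00 by construction.

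**4. The same model simulated** (450 children, 1,000 runs per setting, Wald test at 5%). Each cell gives the odds ratio and the share of runs in which X was detected.

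| Direct log-OR of X | X→duration log-OR | Without duration | With duration |
|---|---|---|---|
| 0 | 1.0 | 1.41, 34% | 1.00, 5% |
| 0 | 1.5 | 1.65, 61% | 1.00, 5% |
| 0.3 | 1.0 | 1.85, 82% | 1.34, 24% |
| 0.3 | 1.5 | 2.18, 94% | 1.35, 23% |
| 0.6 | 1.0 | 2.43, 99% | 1.83, 77% |
| 0.6 | 1.5 | 2.90, 100% | 1.83, 71% |
| 0.6 | 0 | 1.73, 75% | 1.85, 80% |

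The last row is a factor unrelated to duration. It loses nothing.

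**5. A version on the time scale.** Assumptions: time on opioids is 1 day plus an exponential, capped at 14 days, with a median of 3–5 days in the reference half. The factor multiplies the exponential mean by 1.5–2. The doubling hazard is 0.06–0.10 per day after day 1, and a child is tolerant if the doubling precedes the end of opioids. Tolerance is regressed on the factor alone, then on the factor plus duration quartiles.

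| Effect of the factor on the doubling hazard | Detected, factor alone | Detected, duration added |
|---|---|---|
| None | about 33–85% | about 4–7% |
| × 1.5 | about 92–100% | about 54–78% |

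The two data-generating models agree on the pattern. The loss is complete when the effect runs only through duration, partial when there is also a direct effect, and absent when the factor has no link to duration.

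**The case against.** The strongest reply is that the plan has other routes to the same factors. Section 5.4 also admits predictors of secondary outcomes as strata, and duration of exposure is one of those. Section 5.2 plans multivariable models for them. Under the no-direct-effect assumptions of step 5, a regression of log duration on the entry factor detects it in over 90% of runs, more often than the entry-only tolerance model. Section 5.3 also plans unadjusted comparisons by entry factor. This stands as mitigation: a reader might infer that such factors would be lost to the study altogether, and the protocol does not support that. What it leaves open is that neither route gives an entry factor's total association with tolerance, adjusted for the other entry factors. The further regressions in 5.3 for covariates such as age, gender and race refer back to the methods already described, so they do not clearly supply an entry-only model.

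Two further points are fair. Section 5.3 speaks of models built from screened candidates, so duration and drugs are not fixed terms. And concomitant drugs are not all unknown at enrolment, since section 4.2 records first-day use; only later use is unavailable.

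It can also be said that final model content belongs in the analysis plan. Here, however, the protocol itself sets out the candidate list, the screening rule and the use of the result, and the mismatch lies between those statements.

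**Conclusion.** The point holds in a limited form. Sections 5.3 and 5.4 together let factors that cannot be known at enrolment into the tolerance model from which strata may be taken. They also make it likely that entry factors in that model are adjusted for duration.

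The size of the loss depends on effects the protocol does not give. On the assumptions of step 5 it ranges from nearly all of the detectable signal, through a moderate loss, to none. A reader might conclude that adjusted entry factors do no better than chance; that is true only if they have no direct effect on tolerance.

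Nor does this defeat Aim 2, as might be inferred. That aim is to look for and describe risk factors and does not mention stratification, which section 5.4 offers only as a possible later use. The analyses are exploratory, and the incidence endpoint, its precision and the 10-parameter limit are unaffected. This is a cheap and worthwhile improvement, not a fault in the main result.

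**What to change.** In section 5.3, add a separate multivariable model for tolerance limited to variables known at enrolment and already collected under section 4.2. Examples are age, gender, race, body size, PRISM III, diagnostic category, postoperative status, and prior PICU, NICU and surgical history. These ten items fill the 10-parameter limit even at one parameter each, so diagnostic category (21 options) must be collapsed, and race (7 options) collapsed or the list shortened. PRISM III covers the first 12 hours of PICU admission, so it can be a stratum only in a trial that enrols after that window. Report duration and post-entry drug use in their own explanatory analysis.

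In section 5.4, state that only factors known at enrolment are candidates for stratified enrolment, and that the entry model is the source of those for tolerance.

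The cost is one more model and a few sentences, with no new data. The entry model will usually discriminate less well than one that contains post-entry variables.
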